### 3. Expedited Safety Reporting

This option, with 2 possible categories, applies if the adverse event is classified as one of the following:

**Category 1: Serious and unexpected suspected adverse reaction (SUSAR)** (See section [11.3.2. Suspected Adverse Reaction](#) and section [11.3.3. Unexpected Adverse Event](#) and 21 CFR 312.23(c)(1)(i)).

The sponsor shall report any suspected adverse reaction that is both serious and unexpected. The sponsor shall report an AE as a suspected adverse reaction only if there is evidence to suggest a causal relationship between the study drug and the AE, such as:

1. A single occurrence of an event that is uncommon and known to be strongly associated with drug exposure (e.g., angioedema, hepatic injury)
2. One or more occurrences of an event that is not commonly associated with drug exposure but is otherwise uncommon in the population exposed to the drug (e.g., tendon rupture)
3. An aggregate analysis of specific events observed in a clinical trial (such as known consequences of the underlying disease or condition under investigation or other events that commonly occur in the study population independent of drug therapy) that indicates that those events occur more frequently in the drug treatment group than in a concurrent or historical control group

Certain SAEs occur commonly in this study population and will not be considered as a SUSAR unless there is evidence to suggest a causal relationship to the study drug. These events will be captured in the study database but will not be reported as expedited safety reports:

- Food impaction
- Esophageal dilation

#### **Category 2: Any findings from studies that suggests a significant human risk**

The sponsor shall report any findings from other epidemiological studies, analyses of AEs within the current study or pooled analysis across clinical studies or animal or *in vitro* testing (e.g. mutagenicity, teratogenicity, carcinogenicity) that suggest a significant risk in humans exposed to the drug that would result in a safety-

related change in the protocol, informed consent, investigator brochure or package insert, or other aspects of the overall conduct of the study.

The sponsor shall notify the FDA and all participating investigators of expedited Safety Reports within 15 calendar days; unexpected fatal or immediately life-threatening suspected adverse reaction(s) shall be reported as soon as possible or within 7 calendar days.

#### 11.7.4 Reporting of Adverse Events to IRBs/IECs

All investigators shall report AEs, including expedited reports, in a timely fashion to the central IRB in accordance with applicable regulations and guidelines. All FDA safety reports shall be distributed by [REDACTED] or his designee to all participating institutions for site IRB/IEC submission.

#### 11.8 Pregnancy Reporting

The investigator shall be informed immediately of any pregnancy in a study participant as all participants will be receiving drug during this study. A pregnant participant shall be instructed to stop taking study medication immediately, as there are known risks to the fetus as a consequence of the use of losartan potassium. The investigator shall counsel the participant and discuss the risks of continuing with the pregnancy and the possible effects on the fetus. Monitoring of the pregnant participant shall continue until the conclusion of the pregnancy. The investigator shall report all pregnancies to the DAIT/NIAID within 1 business day of becoming aware of the event using the pregnancy paper CRF. All pregnancies identified during the study shall be followed to conclusion, and the outcome of each must be reported. The pregnancy paper CRF shall be updated and submitted to the DAIT/NIAID when details about the outcome are available. When possible, similar information shall be obtained for a pregnancy occurring in a partner of a study participant.

- Information requested about the delivery shall include:
  - Gestational age at delivery
  - Birth weight, length, and head circumference
  - Gender
  - Appearance, pulse, grimace, activity, and respiration (APGAR) score at 1 minute, 5 minutes, and 24 hours after birth, if available
- Any abnormalities

An SAE shall be submitted to the DAIT/NIAID and Study Sponsor ([REDACTED]) using the SAE reporting procedures described above for all pregnancy complications that result in a congenital abnormality, birth defect, miscarriage, or medically indicated abortion.

## 9. Reporting of Other Safety Information

An investigator shall promptly notify the central IRB, as well as the DAIT/NIAID, Study Sponsor (██████████) when an "unanticipated problem involving risks to subjects or others" is identified, which is not otherwise reportable as an AE.

## 10. Review of Safety Information

### 1. Medical Monitor Review

The DAIT/NIAID Medical Monitor shall receive IND annual reports from the sponsor (██████████) compiling new and accumulating information on AEs, SAEs, and pregnancies recorded by the study site(s) on appropriate CRFs.

In addition, the DAIT/NIAID Medical Monitor shall review and make decisions on the disposition of the SAE and pregnancy reports received by the DMCC (See sections [11.7](#), *Reporting of Serious Adverse Events and Adverse Events*, and [11.8](#), *Pregnancy Reporting*).

### 2. DSMB Review

The Data and Safety Monitoring Board (DSMB) shall review safety data at least yearly during planned DSMB Data Review Meetings. Data for the planned safety reviews will include, at a minimum, a listing of all reported AEs and SAEs. The DSMB will be informed of an Expedited Safety Report within 10 days.

#### 1. *Ad hoc* DSMB Reviews

In addition to the pre-scheduled data reviews and planned safety monitoring, the DSMB may be called upon for *ad hoc* reviews. The DSMB will review any event that potentially impacts safety at the request of the protocol chair or DAIT/NIAID and sponsor. In addition, the following events will trigger an *ad hoc* comprehensive DSMB Safety Review:

- Any death that occurs in the study, which is possibly or definitely related to study treatment regimen.
- The occurrence of a Grade 3 or higher related and unexpected SAE in 1 or more of the study participants who have received a study treatment.
- The occurrence of Grade 2 or higher related to the study agent in 2 or more of the study participants who have received study therapy

After review of the data, the DSMB will make recommendations regarding study conduct and/or continuation.

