### 2. Study Oversight

The Study Chair has primary oversight responsibility of this clinical trial. The NIAID/DAIT appointed Data Safety Monitoring Board (DSMB) has oversight responsibility of the Data Safety Monitoring Plan (DSMP) for this clinical trial. The DSMB will review accrual, patterns and frequencies of all adverse events, and protocol compliance annually. The DSMB makes recommendations to the NIH regarding the continuation status of the protocol.

Each site's Principal Investigator and their research team (co-Investigators, research nurses, clinical trial coordinators, and data managers) are responsible for identifying adverse events. Aggregate reports – detailed by

severity, attribution (expected or unexpected), and relationship to the study drug/study procedures – will be available from the DMCC for site review. Adverse events will be reviewed on a monthly basis by the research team and NIAID Medical Monitor. A separate report detailing protocol compliance will also be available from the DMCC for site and NIAID Medical Monitor review on a monthly basis. The research team and NIAID Medical Monitor will then evaluate whether the protocol or informed consent document requires revision based on the reports.

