### 11.7 Reporting of Serious Adverse Events and Adverse Events - RDCRNA Adverse Event Data Management System (AEDAMS)

The site investigator will report by entry into the Adverse Event Data Management System (AEDAMS) all serious adverse events (See section [11.3.4](#), *Serious Adverse Event*), regardless of relationship or expectedness within 24 hours of discovering the event. Notification is by e-mail.

Upon entry of a serious adverse event, the DMCC created Adverse Event Data Management System (AEDAMS) will immediately notify the Study Chair, site PIs and the NIAID Medical Monitor of any reported adverse events via email.

Serious adverse events: The NIAID appointed Medical Monitor (MM) determines causality (unrelated, possibly related, definitely related) of the adverse event. The MM and sponsor, [REDACTED], may request further information if necessary and possibly request changes to the protocol or consent form as a consequence of the adverse event. A back-up notification system is in place so that any delays in review by the MM beyond a specified period of time are forwarded to a secondary reviewer. The Adverse Event Data Management System (AEDAMS) maintains audit trails and stores data (and data updated) and communication related to any adverse event in the study.

Non-serious expected adverse events: Except those listed above as immediately reportable, non-serious expected adverse events that are reported to or observed by the investigator or a member of his/her research team will be submitted to the DMCC in a timely fashion (within 20 working days). The events will be presented in tabular form and given to the MM monthly or on an as needed basis but no less than biannually. Local site investigators are also required to fulfill all reporting requirements of the central IRB.

The DMCC will post aggregate reports of all reported adverse events for site investigators and IRBs.

OR  
[REDACTED]

[name]  
[name]

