**Contact Information for NIAID Medical Monitor:**

[REDACTED]  
Allergy, Asthma and Airway Biology Branch, DAIT, NIAID  
Department of Health and Human Services  
National Institutes of Health  
[name]  
[name]  
[REDACTED]

The SAE should be reported to the Sponsor within 24 hours with as much of the above information as available at that time. All initial and follow-up SAEs should be reported to the Sponsor.

Occasionally, SAEs that occur during a study are unresolved at the time that the participant's study participation ends. SAEs are to be followed to resolution; until they resolve, disappear, or become stable. It is important for the investigator to realize that SAEs may occur in a study participant after the study follow-up period is complete, but that these SAEs still merit reporting in the AEDAMS. The investigator, together with the sponsor and NIAID Medical Monitor, will try to determine whether the SAE is related to the study agent.

All other (suspected) reportable AEs must be reported to the GDCRN by entering into the AEDAMS within **20 working days** of the notification of the event or of the site becoming aware of the event.

Central IRB requirements, and any GDCR oversight committee, remain the responsibility of the treating physician. Reporting to the FDA is the responsibility of [REDACTED] (sponsor).

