### 11.11 Temporary Suspension of Enrollment/ Drug Administration for *Ad Hoc* DSMB Safety Review

(See section [10.2](#), *Participant Stopping Rules and Withdrawal Criteria*)

A temporary halt in enrollment and/or drug administration will be implemented if an *ad hoc* DSMB safety review is required. In this context, no new participants would be consented until the safety review is completed. No additional procedures would be planned during the review, save for those necessary for regular patient care.

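### The ad hoc DSMB trigger for Grade 2 or higher related events in 2 or more participants names no event type and, read as adverse events, has no timely data feed

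*Protocol*

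**What the plan says.** Protocol 11.10.2 (Ad hoc DSMB Reviews) lists three events that call an unscheduled DSMB safety review. The third is: "The occurrence of Grade 2 or higher related to the study agent in 2 or more of the study participants". No noun follows the grade. Under 11.11 such a review has a consequence: "A temporary halt in enrollment and/or drug administration will be implemented". Table 6 (11.5.1) counts both possible and definite attribution as related.

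The reporting clocks are in 11.7:

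- **SAEs** are entered in AEDAMS "regardless of relationship or expectedness within 24 hours of discovering the event", with immediate e-mail to the Study Chair, the site investigators and the Medical Monitor.
- **Non-serious expected AEs** "will be submitted to the DMCC in a timely fashion (within 20 working days"). They are then tabulated and "given to the MM monthly or on an as needed basis but no less than biannually".
- **Other reportable AEs** have the same limit: "All other (suspected) reportable AEs must be reported to the GDCRN by entering into the AEDAMS within" 20 working days of notification or site awareness. No interval for passing these on is stated in 11.7.

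Section 11.2 gives a different review frequency: "Adverse events will be reviewed on a monthly basis by the research team and NIAID Medical Monitor". Section 11.10.1 mentions only annual IND reports and SAE and pregnancy reports for the Medical Monitor. In 11.10.2 the DSMB itself "shall review safety data at least yearly during planned DSMB Data Review Meetings". No section says who counts participants against the Grade 2 trigger, or how soon a halt must follow the second one. The SAP does not mention the trigger.

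**The concern.** A pausing rule works only as fast as the data that feed it. If this trigger counts AEs, a related Grade 2 event that is not serious counts towards it, yet the 24-hour route is for SAEs only. The count also runs across participants and sites, so two sites could each hold one qualifying event, each within its entry limit, and nobody would be obliged to notice that the threshold had been reached.

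The rule exists to protect other participants on drug and people not yet enrolled. Section 6.1.2 refers to six subjects already enrolled, so entry is staggered and a late halt leaves later entrants exposed for longer. The protocol itself treats moderate rises in creatinine, potassium, AST or ALT as important, since 6.4 withdraws the participant. Unless such a rise is serious, it has no expedited entry.

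**Working it through.** **Inputs**

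- Treatment: 4 weeks titration + 12 weeks maintenance (Synopsis) = 16 weeks = 112 days, which agrees with the stated duration.
- Entry limit: 20 working days (11.7). With a five-day week and no holidays, 20 / 5 × 7 = 28 calendar days.
- Passing to the Medical Monitor: monthly, taken as 30.4 days; or the minimum in 11.7, read as twice a year, 182.5 days.
- Sample size: 15 (12.5).

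The documents give no detection time for the trigger, so there is no planned figure to reproduce.

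**Longest lag from site awareness to the Medical Monitor** = entry limit + one full reporting interval.

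| Route | Lag | Share of 112 days |
|---|---|---|
| Monthly | 28 + 30.4 = about 58 days | 58 / 112 = 52% |
| Twice-yearly minimum | 28 + 182.5 = about 210 days | 210 / 112 = 188% |

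**When recognition can fall after the participant's own Week 16**

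- Monthly: only for events after day 112 − 58.4 = 53.6, about day 54. An event at Week 4 (day 28) is recognised by day 28 + 58 = 86, about Week 12, while that participant is still on drug.
- Twice-yearly minimum: an event on the first day can be recognised about 210 − 112 = 98 days (14 weeks) after treatment ends.

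**Typical rather than worst case.** Assume onset is uniform over 112 days and that the event falls at a random point in the reporting cycle. The share of events recognised after that participant's Week 16 is the mean of min(delay, 112) divided by 112.

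- Monthly, entry always at the limit: (28 + 15.2) / 112 = 39%.
- Monthly, entry uniform over 0 to 28 days: (14 + 15.2) / 112 = 26%.
- Twice yearly, by simulation: 83% and 76% respectively.

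These shares follow one event. For the trigger, the relevant lag is that of the second participant's event.

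**Is the trigger likely to be met?** The chance that at least 2 of 15 have a qualifying event is 1 − (1 − p)^15 − 15p(1 − p)^14. The rates p are assumptions. The first borrows the any-grade drug-related figure that 1.5 cites from a paediatric proteinuria trial.

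| p | Chance |
|---|---|
| 5.3% | 19% |
| 10% | 45% |
| 20% | 83% |

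**For contrast**, the 24-hour route with its automatic e-mail would give a lag of about 1 day.

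**Not computable.** Accrual rate and time to convene the DSMB are not stated, so neither the number still on drug at the halt nor the full time to the halt can be derived.

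**The case against.** The other side has several good points.

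- **The missing noun could be SAE.** The bullet just above in 11.10.2 concerns SAEs, and if this one does too, the 24-hour route applies and the timing problem disappears. The AE reading is more natural, because a rule needing two related SAEs adds nothing to 10.5, which suspends the study for one. That argument is not conclusive, since the Grade 3 SAE bullet also overlaps 10.5. The text needs the word.
- **The twice-yearly minimum is narrow.** It covers non-serious expected events only. A reader might infer that all the drug's known risks take the 210-day route. The documents do not support that. Under 11.3.3 an event is unexpected if it is not listed at the observed severity or rate. Section 5.2 lists only minor creatinine increases, in under 0.1% of patients with essential hypertension treated with losartan alone, whereas 6.4 withdraws above 1.5 times the upper limit. Such rises would probably count as unexpected. They still have 20 working days for entry.
- **Monthly review may govern.** Section 11.2 requires it, and 11.7 allows transfer as needed. A reader might infer that the halt comes only after everyone exposed has finished treatment. On the monthly route that does not follow, as the Week 4 example shows. Both lags also add two maxima.
- **Sites are not blind to each other.** Sections 11.2 and 11.7 provide aggregate reports by severity and relationship. These show only what has been entered, so they do not shorten the first 28 days, and they assign the count to nobody.
- **Individuals are protected sooner.** Calls (8.3, 8.5, 8.7), scheduled laboratory tests (8.4, 8.6) and the dose and withdrawal provisions of 6.4 do not wait for the trigger. The protocol chair can also request a DSMB review of any event that may affect safety. This stands, and it limits the point to the study-level halt. Section 11.11 leaves open whether that halt covers dosing as well as enrolment.

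**Conclusion.** The point holds in a limited form. The trigger does not say which events it counts. Read as AEs, it depends on non-serious events that sites may enter up to about 28 calendar days after awareness, and two sections disagree on how often the Medical Monitor then sees them. The longest lag is about 58 days if monthly review governs, and about 210 days for expected events at the twice-yearly minimum, against 112 days of treatment. These figures assume the AE reading, a five-day working week, full use of each limit, and biannual meaning twice a year.

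Under monthly review, late recognition is a problem mainly for events in the second half of treatment. What is delayed is the study-level pause that protects other and later participants, not the care of the person with the event. The size of that loss cannot be stated without the accrual rate. It is worth correcting because the rule is already in the protocol and the remedy is small.

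**What to change.** 1. In 11.10.2, state the event type that the Grade 2 trigger counts: AEs, or whichever type is intended. If only SAEs are intended, the existing 24-hour route already serves and item 2 is not needed.
2. In 11.7, have sites enter any Grade 2 or higher AE they judge possibly or definitely related through the existing AEDAMS 24-hour entry, with its automatic e-mail to the Medical Monitor.
3. Have the DMCC keep the running count of participants with a qualifying event and notify the Medical Monitor when it reaches 2.
4. Reconcile 11.7 with 11.2 by replacing the reporting frequency in 11.7 with: at least monthly, and additionally as needed. Merely deleting the twice-yearly clause would not do, because monthly or as-needed transfer would remain with no firm minimum.

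The cost is wording in two sections, an alert rule in an existing system, and faster entry of a small number of events in about 15 participants. No dose, withdrawal rule or trigger threshold changes.

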### 11.11 Temporary Suspension of Enrollment/ Drug Administration for *Ad Hoc* DSMB Safety Review

(See section [10.2](#), *Participant Stopping Rules and Withdrawal Criteria*)

A temporary halt in enrollment and/or drug administration will be implemented if an *ad hoc* DSMB safety review is required. In this context, no new participants would be consented until the safety review is completed. No additional procedures would be planned during the review, save for those necessary for regular patient care.

## 12 Statistical Considerations and Analytical Plan

### 1. Overview

Change from baseline for eosinophil counts will be calculated for each participant. The average change from baseline within each group and combining both groups (i.e. EoE and EoE-CTD) will be calculated along with the corresponding two-sided, 95% confidence interval. The last observation carried forward (LOCF) method will be used for participants who end the trial early. To assess changes over time for continuous secondary and safety outcomes, a mixed effects model for repeated measures analysis will be used. Unless stated otherwise, all statistical testing will be done at  $\alpha=0.05$ .

### 2. Outcomes

#### 1. Primary Outcomes

- Change from baseline in the peak esophageal eosinophil count in participants receiving losartan at the EOT visit (or at early withdrawal) as determined by EGD with biopsy and reported eosinophils/HPF

#### 2. Secondary Outcomes

- Change from baseline in the blood (serum) and esophageal TGF- $\beta$  levels in participants receiving losartan at the EOT visit (or at early withdrawal) as determined by research blood samples and EGD with biopsy, respectively.
- Normalization of the EoE transcriptome in participants receiving losartan at the EOT visit (or at early withdrawal) as determined by EGD with biopsy.
- Change from baseline in histopathology in participants receiving losartan at the EOT visit (or at early withdrawal) as determined by EGD with biopsy.
- Change from baseline esophageal compliance in participants receiving losartan at the EOT visit (or at early withdrawal) as determined by EndoFLIP.
- Change from baseline PROS (Pediatric Eosinophilic Esophagitis Symptom Severity [PEESS], PedsQL Eosinophilic Esophagitis Module [PedsQL™ EoE], EoE Quality of Life Questionnaire, and EEsAI) in participants receiving losartan at the EOT visit (or at early withdrawal).

### 3. Measures to Minimize Bias

All eligible participants will be assigned to take the losartan. The investigator or designee physician will calculate the losartan dose according to the titration schedule on the basis of the participant's weight. The investigational pharmacist will dispense and prepare the study agent for administration. The DAIT/NIAID, investigator, study staff, and participant will have knowledge of the dose.

### 4. Analysis Plan

Change from baseline for eosinophil counts will be calculated for each participant. The average change from baseline within each group and combining both groups (i.e. EoE and EoE-CTD) will be calculated along with the corresponding two-sided, 95% confidence intervals. If the assumption of normality is not viable for the change from baseline score, we will use a square root transformation on the eosinophil counts prior to calculating the change from baseline and determine if the "change score" attains normality. If this transformation is not successful, the median of the change will be calculated along with the 95% confidence interval for the median using Hodges-Lehmann estimators. Each confidence interval will be visually inspected to determine if zero is a possible value for the true change from baseline ( $\mu$ ). This corresponds to testing the following hypothesis:

$H_0: \mu=0$  vs.  $H_1: \mu \neq 0$ .

The last observation carried forward (LOCF) method will be used for participants who end the trial early.

To assess changes over time for continuous secondary and safety outcomes, a mixed effects model for repeated measures analysis will be used. The dependent variable will be the change from baseline. The "participant nested within group" term will be considered a random effect. Time (i.e. measurement time) will be included as a continuous effect. Terms in the model will be time, group (i.e., EoE and EoE-CTD), and time-by-group interaction. The baseline value will be used as a covariate in the model. If necessary to meet the assumptions of the analysis, an appropriate transformation will be used (e.g., square root, log, rank). The hypotheses that will be tested are whether there is a significant trend over time and whether this trend is consistent between the CTD and non-CTD groups (i.e. testing the interaction term). If the trend is not consistent between groups based on the statistical test at  $\alpha=0.10$ , we will estimate the trend within each of the two groups by including terms in the statistical model that estimates the trend within each group and the hypothesis to be tested within each group is whether this trend is significantly different than zero. We will systematically assess the residuals to determine whether a linear or quadratic model best fits the data. In statistical terms, the hypotheses are provided below.

For testing consistency of the time trend ( $\beta$ ) between the CTD and non-CTD group, the hypotheses are:

$H_0: \beta_{EoE-CTD} = \beta_{EoE(non-CTD)}$  vs.  $H_1: \beta_{EoE-CTD} \neq \beta_{EoE(non-CTD)}$ .

For testing linear trend combining across groups (if there is consistency of the time trend):

$H_0: \beta=0$  vs.  $H_1: \beta \neq 0$

where  $\beta$  is the slope of the line across groups. Similar hypotheses will be tested if analysis of the residuals indicates that higher order terms need to be included in the model (e.g. quadratic). If there is strong evidence that the time trend is not consistent between the two groups, we will test the above hypothesis within each of the two groups. In addition, the two-sided, 95% confidence interval for the slopes will be calculated to provide estimates of the slope for future studies.

The percentage of participants for whom peak eosinophil counts are  $< 15$  eosinophil/HPF at Week 16 will be estimated within each CTD group along with a 95% confidence interval.

Safety endpoints that are categorical will be summarized within each group. Further, any SAEs or Grade 3 or above will be reported descriptively.

All analyses will be performed using SAS version 9.2 or later (Cary, NC).

